5.1 Screening Visit

During the screening visit, eligibility is assessed (based on inclusion/exclusion criteria) and those eligible and interested in participating will provide informed consent. Potential cases will be identified by screening endoscopy and clinic schedules. This will require approval of a limited HIPAA waiver to access the personal health information (PHI) of potential research subjects prior to their formal enrollment.

The following procedures will be completed during the screening visit:

- Informed consent
- Inclusion/exclusion criteria review to determine eligibility
- Demographics
- Medical history
- Current medications
- Vital signs

- Questionnaires
- Blood collection
- EGD with EREF score and biopsies for pathology, per routine care, and biopsies for research purposes***
- Adverse events
- CRF completion

***If subjects have had an EGD at UNC within 3 months of enrollment including clinical and research biopsies that can be used in this study, then the EGD will not be performed and biopsies and EREF scores from the recent EGD will be used in this study.

5.1.1 Consenting Procedure

If a subject is screened eligible and interested in the study, the subject will be consented on the study prior to any study procedure. Written informed consent will be obtained by qualified study personnel. Documentation of the consent process will be maintained in the subject's research record.

Subjects will be given ample time to review the consent document and ask any questions they may have. A copy of the written consent form will be provided to the subject and the original maintained in the subject's research record.

If subjects meet all inclusion and none of the exclusion criteria and consent to the study, they will be enrolled in the study. Subjects will be assigned a unique subject code.

5.1.2 Biopsy Collection and Processing

The research biopsy protocol below is frequently used in CEDAS research projects. If subjects have had an EGD with biopsies at UNC within 3 months prior to enrollment and the biopsies are available for use in this study, and the subject consented to their use in future research studies, then the subject does not need to return for an EGD with biopsies, unless necessary for routine care.

If subjects have not had an EGD within 3 months of enrollment in which biopsies below are available for this study, then they can be scheduled for a routine care EGD with biopsies at UNC to be eligible for this study. However, in some cases, samples that were obtained prior to this time frame can be used, as long as the samples were obtained when the EoE was active and there were no major changes in clinical status. During the routine care EGD, clinical biopsies will be obtained for pathology assessment. In addition, 4 research-specific biopsies will be obtained from each of the following locations: Distal esophagus (3cm from TGF), middle esophagus (8cm from TGF), and proximal esophagus (13cm from TGF). Additionally, 2 research-specific biopsies will be obtained from the duodenum, and 2 research-specific biopsies will be obtained from the stomach (1 from antrum, 1 from body). The 4 distal biopsies will be separated into 4 cryovials: 2 filled with formalin for histology, 1 filled with RNALater, and 1 empty to be frozen immediately in liquid nitrogen.

Research biopsies will be used in this study, and will be stored indefinitely for future research. Subjects will sign a separate stored specimens consent form for this purpose. If a complete set of clinical and research biopsies is not collected during the routine care EGD, then the subject will be considered a screen fail.

Research Related Biopsy Collection Protocol:

| Biopsy Location | Description | Processing/Labeling Instructions |
|---------------------------|---|--|
| 4 distal esophageal (d) | 4 single biopsies 3cm from GEJ  | 2 formalin (h): 
 Label: PID_eh_d1 and PID_eh_d2 + collection date 1 RNALater (r): Refrigerate, store long term in -80deg.F 
 Label: PID_er_d + collection date 1 frozen (f): 
 Label: PID_ef_d + collection date |
| 4 mid esophageal (m) | 4 single biopsies 8cm from GEJ  | 1 formalin (h): 
 Label: PID_eh_m + date 1 RNALater (r): 
 Label: PID_er_m + date 2 frozen(f): 
 Label: PID_ef_m + date and PID_ef_m2 + date |
| 4 proximal esophageal (p) | 4 single biopsies 13cm from GEJ  | 2 formalin (h): 
 Label: PID_eh_p+ date and PID_eh_p2 + date 1 RNALater (r): 
 Label: PID_er_p + date 1 frozen (f): 
 Label: PID_ef_p + date |

Participant IDs (PIPs) will be assigned in numerical order and follow the convention of ID-###. For example, the first person enrolled will be assigned a PIP of ID-001.

Missed biopsies will not be considered protocol deviations or violations.

5.1.3 Blood Sample Collection and Processing

Blood samples will be collected and used in this study, and will be stored indefinitely for future research studies. Subjects will sign a separate stored specimens consent form for this purpose.

| Items | Processing |
|--------------------------|---|
| 6 - 5 mL green top tubes | Hand to PI or representative upon collection Label: PID and collection date Example: ID-001 08Feb16 |

The following blood samples should be collected only if the subject has no research blood samples previously collected during a recent EGD (within 3 months of enrollment) that can be used in this study.

| Items | Processing |
|---|--|
| The following blood samples should be collected only if the subject does not have these samples previously collected from a recent EGD (within 3 months of enrollment) and available for use in this study. | |
| 2 red tops | Spin, aliquot serum into 9 cryovials Label: PID_s# and collection date Example: ID-001_s1 08Feb16 |
| 1 yellow top | Spin, aliquot plasma into 9 cryovials Label: PID_p# and collection date buffy into 1 cryovial Label: PID_b# |
| 1 purple top | Aliquot whole blood into 1mL aliquots – minimum of 3 cryovials Label: PID_w# and collection date |
| 1 PAXgene RNA blood | Room temp at least 2 hours, then freeze Label: PID and collection date |

Participant IDs (PIDs) will be assigned in numerical order and follow the convention of ID-###. For example, the first person enrolled will be assigned a PID of ID-001.

Missed blood samples will not be considered protocol deviations or violations.

5.2 Day 1 Visit

Two weeks prior to the day 1 visit, and while the lab performs T-cell and IgG4 signatures testing, subjects will be asked to fill out the Dysphagia Symptom Questionnaire (DSQ). The DSQ is a daily 3-question symptom diary to be completed nightly over a 2 week time period. This can be done on paper or by email.

During the day 1 visit, subjects will be scheduled for a routine care nutrition counseling appointment. During this appointment subjects will be advised how to effectively follow an elimination diet based on the specific triggers identified between Screening and Day 1 using samples obtained for the research study and will undergo allergy skin prick testing as a research procedure. Results from the allergy skin prick testing will not be used to drive the food elimination diet.

Subjects will be instructed to eliminate between 1 and 5 foods (dairy, wheat, egg, soy, and/or nuts) based on results from the T-cell and IgG4 signatures. Subjects will adhere to the elimination diet for 6 weeks

The following procedures will be completed during the day 1 visit

- DSQ (started 2 weeks prior to day 1 visit)
- Current medications
- Adverse events
- Nutrition counseling as per routine care
- Begin 6 week diet elimination therapy
- CRF completion

5.3 6 Week Follow-Up Visit (+/- 7 days)

Two weeks prior to the 6 week follow-up visit, subjects will be asked to fill out the Dysphagia Symptom Questionnaire (DSQ). The DSQ is a daily 3-question symptom diary to be completed nightly over a 2 week time period. This can be done on paper or by email.

After completion of the 6 week food elimination diet, subjects will return to one of the UNC endoscopy centers and undergo repeat EGD for routine care. During the EGD, clinical biopsies will be obtained. No research biopsies are collected for this study during the 6 week follow-up EGD. Follow up blood samples are collected. Subjects will complete the same questionnaires as the screening visit.

The following procedures will be completed during the 6 week follow-up visit

- DSQ (started 2 weeks prior to 6 week follow-up visit)
- Vital Signs
- Questionnaires
- EGD with EREF score and biopsies for pathology, per routine care (no research biopsies are obtained at the 6 week follow-up visit for this study)
- Blood collection
- Adverse events

Study participation is complete after completion of the 6 week follow-up visit.

6 Statistical Plan

6.1 Sample Size Determination

Because this is a proof-of-principle effectiveness study without a comparison group, there is not a formal sample size calculation. However, we plan to consent and enroll up to 30 subjects with a goal of 20 subjects completing the study to show that 75% (15) have a histologic response to the allergen-specific immune-signature dietary elimination. We feel that this is a robust number of patients to demonstrate a preliminary effect, while also being a realistic number to enroll during this pilot study. In addition, while the 95% CIs around this goal are somewhat wide (47-92%), current allergy testing only has the ability to accurately predict triggers 13% of the time, so even if we are at the lower end of the range, it's still a major clinical step forward in practice.

In the proposed study, we will be performing the first prospective effectiveness study of an allergen-specific immune signature-based individualized dietary elimination regimen in patients with EoE. Because we are conducting what will essentially be a pilot or proof-of-principle study, the data we collect, including response rates and magnitude of response, will directly inform a planned large scale (ie R01) grant application for a randomized study of immune-signature-based elimination versus empiric food elimination.

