|------------------------|-----|-----|-----|-------|------|
| Testing parameters (%) | | | | | |
| Sensitivity | 100 | 100 | 75 | 80 | 64 |
| Specificity | 50 | 50 | 45 | 43 | 25 |
| Agreement | 60 | 75 | 53 | 58 | 53 |

These thresholds will be used in this prospective study of allergen-specific immune signature-guided dietary elimination therapy to assess the clinical effectiveness of this technique. Samples may be tested using additional allergens, including but not limited to beef, corn, fish, shellfish, rice, chicken, potato, pork,

legumes, green beans, tomatoes, green peppers, and tree nuts. Results from these additional allergens are for data collection only and will not be used to drive subject diet elimination or communicated to subjects.

2 Study Objectives

Primary Objective: To evaluate prospectively the effectiveness of individualized allergen-specific immune signature-based dietary elimination therapy for EoE.

We hypothesize that at least 75% of patients with active EoE will experience a histologic response following treatment with an individualized dietary regimen based on their own allergen-specific immune signature.

3 Study Design

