6.2 Statistical Methods

To determine the response rate for the primary outcome, the number of subjects with <15 eos/hpf on follow-up endoscopy will be calculated. For secondary outcomes, median eosinophil counts, endoscopy scores, and symptoms scores will be compared before and after treatment with Wilcoxon signed-rank. These will be contextualized by calculating odds ratios and 95% confidence intervals where appropriate, so as not to

over-rely on p values alone. Patients who drop out or who have incomplete data for the outcomes will be excluded from analysis. Because this study's outcomes are determined after the treatment period and follow-up endoscopy, a subject must complete this end of treatment evaluation for us to be able to include their data in the analysis. We do not feel that selection bias would impact the analysis if there are incomplete data due to drop out. We are not performing a comparative analysis between groups, so drop out would not be dependent on different treatments administered in different study arms. In addition, in our experience with previous clinical studies of EoE, dropout rates have been quite low.

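### Twenty completers can estimate the histologic response rate but cannot show it is at least 75%; the printed interval of 47-92% is not the interval for 15/20

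*Combined protocol and SAP*

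**What the plan says.** Section 2 (Study Objectives) gives the hypothesis: "We hypothesize that at least 75% of patients with active EoE will experience a histologic response" on a diet guided by their own immune signature. Section 6.1 (Sample Size Determination) states that "there is not a formal sample size calculation", because the study is a proof-of-principle study with no comparison group. It sets an enrolment ceiling of 30 and gives the purpose of the sample in these words: "with a goal of 20 subjects completing the study to show that 75% (15) have a histologic response". It describes this number as robust for a preliminary effect.

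The only inferential figure is the interval, in per cent, in the remark "while the 95% CIs around this goal are somewhat wide (47-92". The section defends that width on the ground that "current allergy testing only has the ability to accurately predict triggers 13% of the time", so that even the lower end would be an advance.

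Section 6.2 (Statistical Methods) says of the primary outcome only that "the number of subjects with <15 eos/hpf on follow-up endoscopy will be calculated". No null rate, test, significance level, power or success count is given. Section 7.4 rules out an interim analysis, and section 6.3 restricts the analysis to subjects with complete outcome data.

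**The concern.** The number 20 is justified by what it is meant to show, and the hypothesis concerns the rate among patients with active disease, not the proportion in this sample. A reader who puts sections 2 and 6.1 together may take 15 responders in 20 as confirmation of the hypothesis and 14 as failure. A sample of 20 supports neither conclusion.

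This matters because section 6.1 says that the response rates will feed directly into a grant application for a randomised comparison with empiric elimination. Quoting 15/20 there as demonstrating at least 75% would overstate the evidence. Treating 14/20 as a negative result would discard data compatible with 75%: its exact 95% interval is 46-88%. The printed interval could also be carried forward as the precision of 15/20, which it is not.

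**Working it through.** **Inputs.** From section 6.1: n = 20 completers, target r = 15, stated 95% interval 47-92%. From section 2: hypothesised rate at least 75%. From section 7.4: no interim look, so a single-stage binomial applies.

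**1. The plan's own figures.** The count reproduces: 0.75 × 20 = 15. The interval does not. For 15/20, eight methods give these 95% limits:

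| Method | Lower % | Upper % |
|---|---|---|
| Exact (Clopper-Pearson) | 51 | 91 |
| Wilson | 53 | 89 |
| Wilson, continuity-corrected | 51 | 90 |
| Wald | 56 | 94 |
| Wald, continuity-corrected | 54 | 96 |
| Agresti-Coull | 53 | 89 |
| Jeffreys | 54 | 90 |
| Inverted exact test | 53 | 90 |

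None has a lower limit below 50%. The printed pair does match the continuity-corrected Wilson interval for 12/16 (47.4-91.7%), which also has a point estimate of 75%. The exact interval for 12/16 is close (47.6-92.7%). A base of 16 is therefore a possible origin, but that is an inference; the documents do not say how the interval was obtained.

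**2. What 15/20 supports.** The exact limits are beta quantiles:

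- lower = Beta quantile(0.025; r, n − r + 1) = Beta(0.025; 15, 6) = 0.509
- upper = Beta quantile(0.975; r + 1, n − r) = Beta(0.975; 16, 5) = 0.913

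As a check, P(X ≥ 15) at a true rate of 0.509 and P(X ≤ 15) at 0.913 are each 0.025. Meeting the goal is thus compatible with true rates from about 51% to 91%. The plan's own lower limit of 47% leads to the same conclusion.

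**3. How often the goal is reached.** P(X ≥ 15) = Σ C(20, k) p^k (1 − p)^(20 − k), for k = 15 to 20. At p = 0.75 the terms are 0.2023 + 0.1897 + 0.1339 + 0.0669 + 0.0211 + 0.0032 = 0.617 after rounding. So the goal is missed with probability 1 − 0.617 = 0.383 when the true rate is exactly 75%. At other assumed true rates:

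| True rate | P(at least 15/20) |
|---|---|
| 60% | 0.13 |
| 65% | 0.25 |
| 70% | 0.42 |
| 75% | 0.62 |
| 80% | 0.80 |
| 85% | 0.93 |
| 90% | 0.99 |

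Only the 75% row uses a rate given in the plan; the others show the range. The 70% row is a case where the hypothesis is false yet the goal is met in about two trials of five.

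**The case against.** The strongest reply is that the plan never claims the property being tested. It disclaims a formal calculation, calls itself a pilot, specifies no test, and says in the same paragraph that the interval is wide and may reach 47%, which is less favourable than the correct 51%. On this view the verb in section 6.1 is loose wording, and a probability near 0.6 is unsurprising when a target count equals its expected value. Within the hypothesis the chance of reaching 15 rises quickly, to 0.80 at a true rate of 80% and 0.93 at 85%.

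Much of this stands. The 0.62 is the chance of meeting an informal goal, not the power of a planned test, and a pilot may state a hypothesis it is not sized to test. What does not stand is the wording of the goal, which follows directly on the disclaimer, and the interval, which does not belong to 15/20. Nor does the comparison with 13% answer the point: that figure is the accuracy of trigger prediction, not a histologic response rate, and it says nothing about whether the rate is at least 75%.

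Two stronger readings are tempting, and the documents support neither.

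- *A reader might infer that 15/20 is the trial's success rule, or that 19/20 is required.* It is true that the exact lower limit first passes 75% at 19/20 (75.1%; 18/20 gives 68.3%). But that threshold belongs to a test against 75% that the plan does not contain, and no conclusion in section 6 is tied to any count.
- *A reader might infer from Table 4 in section 1.2 that 75% is out of reach.* The combined-test row reads "Sensitivity | 100 | 100 | 75 | 80 | 64", so milk sensitivity is 64%. Solving agreement = prevalence × sensitivity + (1 − prevalence) × specificity for milk gives (0.53 − 0.25)/(0.64 − 0.25) = 0.72, and full trigger removal would seem capped at 1 − 0.72 × 0.36 = 0.74. The same calculation gives impossible prevalences in the neighbouring tables: 1.04 for milk in Table 2, and −0.39 for nut and 1.56 for soy in Table 3. Nothing in the documents says that one missed trigger prevents a count below 15 eos/hpf. No ceiling on the response rate can be drawn from these tables.

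**Conclusion.** The concern holds as a mismatch between the stated purpose of the sample size and what that size can deliver. With 20 completers, 15 responders give an exact 95% interval of 51-91%. The goal is reached with probability 0.62 at a true rate of 75%, 0.42 at 70%, 0.80 at 80% and 0.93 at 85%. Meeting it does not establish at least 75%, and missing it does not refute that. Separately, 47-92% is not the interval for 15/20.

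These figures assume exactly 20 evaluable subjects, independent outcomes and a common response probability. The point does not show that the trial is too small for a pilot or that its data would be unusable. The enrolment target, endpoint and procedures are unaffected.

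**What to change.** In section 6.1:

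1. Replace the clause about showing a 75% response with: *to estimate the histologic response rate (expected 75%, 15/20)*.
2. Replace 47-92% with the exact 95% interval for 15/20, 51-91%, and name the method.
3. Add that the observed response rate will be reported with its exact 95% confidence interval, based on the number of subjects actually analysed. Repeat this in section 6.2, which at present only counts responders.
4. Add that 15/20 is not a success criterion and does not by itself establish a rate of at least 75%.

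The hypothesis in section 2 can remain, provided section 6.1 makes clear that the study is sized to estimate the rate and not to test it. The cost is wording only: no added subjects, visits or procedures. The drawback is a more modest stated aim.

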| IVD | In-vitro diagnostic |
| NSR | Non-significant risk |
| PID | Participant ID |

Study Summary

| | |
|---------------------------------------|--|
| Title | Application of a Novel Allergen-Specific Immune Signature Directed Approach to Dietary Elimination Therapy in Patients with Eosinophilic Esophagitis (IDiET) |
| Short Title | IDiET |
| Methodology | Prospective single center clinical trial |
| Study Duration | 2 years |
| Study Center(s) | University of North Carolina, Chapel Hill, NC |
| Objectives | To evaluate prospectively the effectiveness of individualized allergen-specific immune signature-based dietary elimination therapy for EoE |
| Number of Subjects | 30 |
| Diagnosis and Main Inclusion Criteria | 
Inclusion Criteria:
 
1) Age 16-80 years old2) Meet one of the following:
a. Active EoE as per consensus guidelines ORb. Undergoing upper endoscopy for a clinical suspicion of EoE3) No prior history of dietary elimination therapy 
Exclusion Criteria:
 
1) Concomitant eosinophilic gastroenteritis2) Any corticosteroid exposure in the 4 weeks prior to their baseline endoscopic exam3) Previous esophageal surgery4) Medical instability that precludes safely performing upper endoscopy5) Inability to read or understand English6) Pregnant women |

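### Section 6.1 prints 47–92% as the 95% confidence interval for 15 responders among 20 completers; the exact interval is 51–91%

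*Combined protocol and SAP*

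**What the plan says.** Section 6.1 (Sample Size Determination) states that "there is not a formal sample size calculation" because the study is a single-group proof of principle. It then gives the numbers on which the size rests. Enrolment is capped at 30, and the target is worded "with a goal of 20 subjects completing the study to show that 75% (15) have a histologic response". The 75% is the hypothesis of section 2 (Study Objectives): "We hypothesize that at least 75% of patients with active EoE will experience a histologic response".

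The next lines of section 6.1 attach a precision statement to that target: "while the 95% CIs around this goal are somewhat wide (47-92" (percent). They go on to argue that "even if we are at the lower end of the range", the result would far exceed the 13% accuracy attributed to current allergy testing. No interval method is named there, and section 6.2 (Statistical Methods) names none for the response rate. Sections 6.2 and 6.3 restrict the analysis to subjects with complete outcome data, so completers are the denominator.

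**The concern.** The interval is tied explicitly to the goal, and the only count pair that describes the goal is 15 of 20. A 95% interval for 15/20 should have a lower limit a little above one half; the printed one lies below one half. A gap of about four points is too large for rounding.

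With no formal sample size calculation, this interval is the only quantitative support for 20 completers, and the text reasons directly from its lower end. If it was computed for a different number of completers, the goal and its stated precision describe different samples. Section 6.1 also says that the response-rate data will inform a later grant application, where a figure that does not reproduce could be noticed.

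**Working it through.** **Inputs (section 6.1).** Completers n = 20; responders x = 15, so p = 0.75; level 95%, taken as two-sided, z = 1.96. Printed interval: 47–92%.

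**Attempt to reproduce the printed figure from 15/20**

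*Clopper-Pearson.* The limits are the beta quantiles B(0.025; x, n−x+1) and B(0.975; x+1, n−x).
- Lower: B(0.025; 15, 6) = 50.9%.
- Upper: B(0.975; 16, 5) = 91.3%.
- Tail check: at a true rate of 47%, P(X ≥ 15 of 20) = 0.0105; at 92%, P(X ≤ 15 of 20) = 0.0183. Both would be 0.025 if 47% and 92% were the exact 95% limits.

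*Wilson with continuity correction.* With q = 1−p:
- L = [2np + z² − 1 − z√(z² − 2 − 1/n + 4p(nq + 1))] / [2(n + z²)]
- U = [2np + z² + 1 + z√(z² + 2 − 1/n + 4p(nq − 1))] / [2(n + z²)]
- L = [30 + 3.84 − 1 − 1.96√19.79] / 47.68 = 24.12 / 47.68 = 50.6%
- U = [30 + 3.84 + 1 + 1.96√17.79] / 47.68 = 43.11 / 47.68 = 90.4%

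*Wald.* 0.75 ± 1.96√(0.75 × 0.25 / 20) = 0.75 ± 0.190, i.e. 56.0–94.0%.

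| Method, 15/20, 95% | Interval (%) |
|---|---|
| Clopper-Pearson | 50.9–91.3 |
| Wilson, continuity-corrected | 50.6–90.4 |
| Wilson | 53.1–88.8 |
| Wald | 56.0–94.0 |
| Wald, continuity-corrected | 53.5–96.5 |
| Agresti-Coull | 52.8–89.2 |
| Jeffreys | 53.6–89.8 |
| Mid-P | 53.0–90.2 |
| Inverted exact binomial test | 52.5–89.6 |
| Logit | 52.2–89.2 |
| Arcsine | 54.3–91.0 |
| Complementary log-log | 50.0–88.7 |

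The lowest lower limit is 50.0%. No method gives 47%.

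**Other explanations**

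- *Enrolled subjects as denominator.* 75% of 30 is 22.5. Clopper-Pearson gives 54–88% for 22/30 and 58–90% for 23/30. Neither fits.
- *Another confidence level.* Continuity-corrected Wilson for 15/20 gives 46.6–91.8% at 98%, which rounds to 47–92. The text says 95%.
- *Another count pair.* A search over every x/n with n from 5 to 60, using the twelve methods at 95%, finds two intervals that round to 47–92. They are 12/16 by continuity-corrected Wilson and 9/12 by Jeffreys (47.1–92.4%). Both are exactly 75%.

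For 12/16 the continuity-corrected Wilson limits are:
- L = [24 + 3.84 − 1 − 1.96√16.78] / 39.68 = 18.81 / 39.68 = 47.4%
- U = [24 + 3.84 + 1 + 1.96√14.78] / 39.68 = 36.38 / 39.68 = 91.7%

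Clopper-Pearson for 12/16 is 47.6–92.7%, which matches only if the decimals are cut off; rounded, it is 48–93%.

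**Size of the discrepancy against Clopper-Pearson for 15/20**

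- Lower limit: 50.9 − 47 = 3.9 points too low.
- Upper limit: 92 − 91.3 = 0.7 points too high.
- Width: 92 − 47 = 45 points printed, against 91.3 − 50.9 = 40.4 points.

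**The case against.** The arithmetic is hard to contest, but its weight can be.

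First, nothing depends on the interval. The study is a pilot without a formal sample size calculation. Section 7.4 has no stopping rule or interim analysis, and sections 6.2 and 6.3 attach no test or success threshold to the interval. The choice of 20 also rests on feasibility. The printed interval is wider at both ends than the exact one, so it understates precision, and the contrast with 13% is the same from 47% or 51%. All of this stands, and it keeps the point minor.

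Second, the 12/16 origin is conjecture. Neither 16 completers nor 12 responders appears in the documents, and 9/12 fits by another method. If truncation is allowed, 10/13 by logit (47.9–92.4%) and 14/20 by continuity-corrected Wald (47.4–92.6%) fit too. A plain slip at n = 20 is equally possible. This stands as well: the 12/16 match is a lead for the sponsor to check, not a finding about the source.

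Third, the plan names no method, so the gap depends on the comparator. Against continuity-corrected Wilson it is 50.6 − 47 = 3.6 points below and 92 − 90.4 = 1.6 points above. That is fair for the size of the gap. It does not rescue the figure, because no 95% method tried gives 47–92% for 15/20.

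**Conclusion.** The concern holds, as a minor arithmetic error. The interval in section 6.1 is not a 95% interval for 15 of 20; the exact one is 50.9–91.3%. The printed lower limit is 3.9 points too low and the printed width about 4.6 points too large (45 − 40.4). The error is conservative and leaves the section's argument intact, but as written the goal and its interval do not describe the same sample.

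The conclusion assumes a two-sided interval and the stated 95% level, with 15/20 as the goal meant. The sizes given are relative to Clopper-Pearson. Confidence in the mismatch is high. The documents cannot settle whether the figure came from 16 completers, from some other number, or from a slip.

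**What to change.** In section 6.1, replace the printed interval with 51–91% and name its basis (Clopper-Pearson, 15 of 20). If a different number of completers was intended, state that number and the method that yields 47–92%, and bring the goal of 20 completers and 15 responders into line with it.

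As an optional clarification, not the correction of an error, section 6.2 and the Study Summary could say that the response rate will be reported as n/N with an exact 95% interval.

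The cost is one number and a method name. Correcting the interval for 15/20 changes no procedure, data collection or sample size.
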